2.2. Secondary Objectives and Endpoints

Secondary Objectives	Secondary Endpoints
To determine the antitumor activity in terms of progression free survival (PFS) and duration of response (DOR) of tipifarnib in subjects with relapsed or refractory PTCL.	
• Progression Free Survival (PFS)• Duration of Response (DOR) with the response assessed according to the Lugano Classification (Protocol Appendix II).
Safety and tolerability of tipifarnib in subjects with relapsed or refractory PTCL.	Treatment-emergent adverse events (TEAE) and serious adverse events (SAEs) evaluated according to NCI CTCAE v.4.03.
Assessment of ORR, PFS, and DOR in study population subgroups defined according to the genetic subtypes.	ORR, PFS, and DOR in subgroups defined by AITL, PTCL-NOS, CXCL12+, and Other.

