For enrollment into the AITL expansion cohort, subjects must have the diagnosis of AITL, nodal PTCL with T-follicular helper phenotype or follicular PTCL.

For enrollment into the CXCL12+ PTCL expansion cohort, subjects must have the diagnosis of PTCL (a – h subtypes listed above, except AITL), consent to provide buccal swabs for CXCL12 SNP testing, and be found to be CXCL12+ based on testing by a Sponsor approved methodology. Once (if) the AITL cohort has completed accrual, subjects with AITL histology and CXCL12+ status may be enrolled in the CXCL12+ PTCL expansion cohort.

3. Subject has relapsed or are refractory to at least 1 prior systemic cytotoxic therapy. Subjects must have received conventional therapy as a prior therapy.
4. Subject has consented to provide at least 6 unstained tumor slides (10 preferred) or an FFPE block for biomarker testing. Tumor tissue may be obtained from prior archival diagnostic biopsies. If the site is unable to confirm during screening that sufficient archival biopsy is available, the subject must consent to a pretreatment biopsy for inclusion in this study.
5. Subject has measurable disease as determined by the Lugano Classification and/or mSWAT.
6. At least 2 weeks since the last systemic therapy regimen prior to enrollment. Subjects must have recovered to NCI CTCAE v. 4.03 < Grade 2 from all acute toxicities (excluding Grade 2 toxicities that are not considered a safety risk by the Sponsor and Investigator) or toxicity must be deemed irreversible by the Investigator.
7. At least 2 weeks since last radiotherapy if radiation was localized to the only site of measurable disease, unless there is documentation of disease progression of the irradiated site. Subjects must have recovered from all acute toxicities from radiotherapy.
8. ECOG performance status of 0-2 ([Appendix 1](#)).
9. Acceptable liver function:
 - a. Bilirubin \leq 1.5 times upper limit of normal (x ULN); does not apply to subjects with Gilbert's syndrome diagnosed according to institutional guidelines.
 - b. AST (SGOT) and ALT (SGPT) \leq 3 x ULN; if liver lymphoma is present, then \leq 5 x ULN is allowed.
10. Acceptable renal function with serum creatinine \leq 1.5 x ULN or a calculated creatinine clearance \geq 60 mL/min using the Cockcroft-Gault or MDRD formulas.
11. Acceptable hematologic status:
 - a. ANC \geq 1000 cells/ μ L.
 - b. Platelet count \geq 50,000/ μ L.

c. Hemoglobin \geq 8.0 g/dL.

12. Female subjects must be:

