2. 12- Lead ECG is to be performed at 2-4 hours post dose on Cycle 1 Day 1 and Cycle 1 Day 7 (Day 7 can occur between days 5-7) only. Additional ECGs may be performed if deemed necessary by the Investigator.
3. Assessment is to be done within 14 days prior to first administration of study drug on Day 1 of Cycle 1.
4. Hematology and chemistry tests do not need to be repeated on Cycle 1 Day 1 if they were conducted within 72 hours prior to the first administration of study drug.
5. Laboratory tests may need to be conducted on additional time points if deemed necessary by the investigator. Samples will be analysed locally at the clinical site. Fasting for chemistry testing is not required.
6. Collection of available archival tumor tissue in a paraffin embedded block or a minimum of 6 unstained slides (10 preferred). The archival tumor tissue(s) can be collected within Cycle 1 if additional time is needed to locate the tissues but must be shipped to the Sponsor (or designee) by the end of Cycle 1. Efforts should be made to collect these materials as early as possible. If the site is unable to confirm during screening that sufficient archival tissue is available, a new biopsy must be taken at any time prior to the initiation of dosing. Buccal swabs will be collected to determine prospectively subject eligibility for enrollment into the CXCL12+ cohort, or retrospectively to determine CXCL12 status in the AITL cohort, using kits provided by the Sponsor. Buccal swabs may be collected at any time (> 28 days screening period) in order to determine eligibility. For Amendment 7, additional genomic assessments beyond the CXCL12 3'UTR gene status may also be obtained from the buccal swabs. The assessments could be conducted to determine whether gene variants observed in tumors are of somatic (not present in a buccal swab) or germinal (present in a buccal swab) origin.
7. [REDACTED]

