A preliminary assessment of the first 50 subjects enrolled into the current trial was recently published (Witzig 2019). In the initial stages of the study, a retrospective assessment had suggested a high-degree of anti-tumor activity of tipifarnib in AITL and in PTCL-NOS subjects whose tumors expressed high levels of CXCL12 and carried reference CXCL12 3'UTR sequences of the CXCL12 gene (Witzig 2017). The median progression-free survival (mPFS) in subjects with reference 3'UTR sequences (n = 8) was 134 days, vs. a median PFS of 50 days (n = 7) in subjects whose tumors expressed the rs2839695 A>G variant of the gene, which resulted in low levels of CXCL12 expression. Based on those findings, a cohort of PTCL NOS subjects with reference CXCL12 3'UTR and a cohort enrolling AITL subjects were added to the trial. These cohorts investigated prospectively whether selection for subjects with high CXCL12 expressing tumors enriches for the activity of tipifarnib. Of 15 subjects enrolled into the PTCL expansion cohort, 12 were evaluable for efficacy at the time of the report. In the per protocol set (PPS, or all subjects who received at least 1 dose of tipifarnib and had 1 post-baseline efficacy assessment) the objective response rate (ORR) was 41.7% (3 CR, 2 PR) and the clinical benefit rate (CBR) was 91.7% (3 CR, 2 PR and 6 SD). Four subjects of AITL histology were enrolled in the cohort. Of the 3 CRs observed, 2 were experienced by AITL subjects.

In the AITL expansion cohort, 16 patients were enrolled with 11 being evaluable for efficacy. The ORR in the PPS was 45.4% and the CBR was 72.7% (3 CR, 2 PR, 3 SD). If all AITL subjects enrolled in the study are considered (expansion cohort subjects plus the AITL subjects in the early phases of the trial, n = 23, 17 evaluable), the ORR was 52.9% and the CBR was 70.6% (5CR, 4PR, 3 SD).

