12.4 Sample Size Determination

A two-stage study design was used in the initial cohort of PTCL subjects without histological or genetic selection in order to minimize the number of study subjects treated if tipifarnib were to be not efficacious. This design is intended to allow the termination of accrual in case of unacceptably low efficacy after the first subjects are evaluated in a Full Analysis Set (FAS) basis.

A two-stage design will be employed. Eleven initial study subjects will be enrolled; if 2-4 responses are observed, 7 additional subjects will be enrolled. At the completion of this cohort, treatment will be considered of further interest if the true ORR is higher than 10%. To determine the total trial size of the initial cohort of subjects, a response of interest of 30% is assumed. This design provides 80% power to detect a difference between 10% and 30% ORR at one-sided significance level of 0.087. Using this design, the probability of terminating the study at the end of stage 1 if the true ORR is 10% is 0.697 while the probability of terminating the study at the end of stage 1 if the true ORR is 30% is 0.113.

An AITL cohort will be enrolled ($N = 12$) according to Amendment 4 to the protocol. With this sample size, if 4 or more responses are observed, the probability that the true response rate in AITL subjects is at least 30% is 82.6% ([Table 6](#)).

Based on the observed antitumor activity during stage 1 and stage 2 of the study in which subjects who were found to have high levels of CXCL12 gene expression and reference CXCL12 3'UTR by retrospective analysis had better outcomes in terms of response and PFS compared to subjects with low CXCL12 expression and CXCL12 3'UTR variant sequences, a CXCL12+ cohort will be enrolled ($N = 12$) according to Amendment 6 to the protocol. With this sample size, if 2 or more responses are observed, the probability that the true response rate in CXCL12+ subjects is 10% or higher is at least 87% ([Table 7](#)).

It is assumed that the presence of CXCL12 3'UTR gene variants is of germinal, not somatic, origin. By default, CXCL12+ subjects are defined as those who present with reference CXCL12 reference gene sequence in a buccal swab assay and in whom no CXCL12 3'UTR variant or

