7. SUMMARY OF STUDY POPULATION DATA

7.1. Subject Disposition

Subject disposition will be provided for all subjects screened. The disposition table will include the total number of subjects screened, total number of screen failures, and total number who received any study drug will be displayed. Among subjects who received any study drug, frequency and percentage of subjects who completed treatment, prematurely discontinued and reasons for premature discontinuation and reason for end of study will be tabulated. Subjects will be presented throughout by their genetic subtype: AITL, PTCL, CXCL12+, and an Other category, which includes one subject that is ALCL-ALK negative and one that is PTCL sub-type not otherwise specified in the protocol.

Detailed subject disposition information, subject eligibility, and analysis population assignment will be displayed in separate listings.

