14. CHANGES IN THE STATISTICAL METHODS FROM THOSE STATED IN THE PROTOCOL

For the efficacy analysis, the estimation of the objective response rate will be estimated for all subjects in the indicated study population and will not be done separately for each tumor histology type evaluated.

An exploratory Efficacy Analysis (to be performed if results warrant) has been added and is described in Section [8.3](#) of this document.

Summaries for hematology and chemistry-related AEs have been added to the safety analysis.

Laboratory change and shift from baseline will not be performed.

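### The secondary subgroups put histology and CXCL12 genotype into one four-level variable, with no rule for subjects who have both attributes and no CXCL12-variant comparator

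*SAP*

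**What the plan says.** SAP 2.2 sets a secondary objective of assessing "study population subgroups defined according to the genetic subtypes", with the endpoint "ORR, PFS, and DOR in subgroups defined by AITL, PTCL-NOS, CXCL12+, and Other". SAP 8.1 and 8.2 repeat the plan for all three endpoints. SAP 8.2 also allows logistic and Cox models to compare the subgroups. SAP 7.1 carries the variable into all displays: "Subjects will be presented throughout by their genetic subtype: AITL, PTCL, CXCL12+, and an Other category". It writes PTCL where 2.2 writes PTCL-NOS.

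The protocol defines the groups on different axes. AITL and PTCL-NOS are diagnoses in the inclusion list (Protocol 7.1). CXCL12+ is a sequence result: "By default, CXCL12+ subjects are defined as those who present with reference CXCL12 reference gene sequence in a buccal swab assay" (Protocol 12.4), with no variant found later in the tumor.

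The protocol lets one subject have both attributes:
- After the AITL cohort has filled, "subjects with AITL histology and CXCL12+ status may be enrolled in the CXCL12+ PTCL expansion cohort" (Synopsis and Protocol 7.1).
- This happened: "Four subjects of AITL histology were enrolled in the cohort" (Protocol 5.2, on the CXCL12+ cohort).
- Buccal swabs are also used "or retrospectively to determine CXCL12 status in the AITL cohort" (Table 1, footnote 6).
- Protocol 5.2 gives 3'UTR results for the early part of the trial: 8 subjects with reference sequence and 7 with the variant.

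SAP 12 says data are summarized by cohort, which is a different grouping again. SAP 14 says that ORR estimation "will not be done separately for each tumor histology type evaluated".

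**The concern.** A single variable with four levels suits attributes that exclude one another. Histology and genotype do not. The SAP has to place a CXCL12+ subject with AITL somewhere, and it gives no rule. The trial is open label and preliminary results by cohort are already in the protocol, so a rule chosen late would be chosen with the responses known.

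The choice also decides what each row estimates. Protocol 5.2 says the expansion cohorts were meant to show whether selecting for high CXCL12 expression enriches for activity. That question needs CXCL12-reference subjects set against CXCL12-variant subjects, with AITL kept apart. The planned rows contain no variant group; variant subjects are spread over the histology rows. A model contrast of AITL with CXCL12+ inside one factor has no clear meaning when some subjects are both.

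**Working it through.** **Inputs (Protocol 5.2 unless noted; a preliminary cut of the first 50 subjects in a per-protocol set defined much like the SAP's full analysis set)**
- AITL cohort: 16 enrolled, 11 evaluable; 3 CR, 2 PR, 3 SD, so 3 others.
- CXCL12+ cohort: 15 enrolled, 12 evaluable; 3 CR, 2 PR, 6 SD, so 1 other. Four enrolled subjects have AITL, and two of the three CRs are theirs.
- Protocol 12.4: 2 of the 5 CXCL12+ cohort responders have AITL.
- All AITL in the trial: 23 enrolled, 17 evaluable; 5 CR, 4 PR, 3 SD, so 5 others.
- Protocol 8.1: the AITL responders in stages 1 and 2 had partial responses.

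**Reproducing the protocol's rates**
- AITL cohort: 5/11 = 45.45% (printed 45.4%).
- All AITL: 9/17 = 52.9%.
- CXCL12+ cohort: 5/12 = 41.7%.

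All three agree with the protocol, apart from rounding.

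**AITL subjects outside the AITL cohort**
- Enrolled: 23 − 16 = 7, which is 7/23 = 30%.
- Evaluable: 17 − 11 = 6, made up of 5 − 3 = 2 CR, 4 − 2 = 2 PR, 3 − 3 = 0 SD and 5 − 3 = 2 others.
- The 2 CRs match the two AITL CRs in the CXCL12+ cohort, so those subjects count in both the 41.7% and the 52.9%.

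**Evaluable AITL subjects in the CXCL12+ cohort (k)**
- They include 2 CR, no PR (both AITL responders are the CRs), no SD, and at most 1 other, because that cohort has only one. So k is 2 or 3.
- Early AITL subjects enrolled: 23 − 16 − 4 = 3, so at most 3 are evaluable. Then 6 − k ≤ 3 and k ≥ 3.
- Hence k = 3. The 17 split as 11 + 3 + 3 and the 9 responders as 5 + 2 + 2.

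**What the grouping does to the rates**

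Exact 95% limits are the Beta quantiles B(0.025; x, n − x + 1) and B(0.975; x + 1, n − x).

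| Group | x/n | ORR | Exact 95% CI |
|---|---|---|---|
| AITL, by cohort | 5/11 | 45.5% | 16.7 to 76.6 |
| AITL, all by histology | 9/17 | 52.9% | 27.8 to 77.0 |
| AITL, early subjects left out: (9 − 2)/(17 − 3) | 7/14 | 50.0% | 23 to 77 |
| CXCL12+, as enrolled | 5/12 | 41.7% | 15.2 to 72.3 |
| CXCL12+ cohort, AITL left out: (5 − 2)/(12 − 3) | 3/9 | 33.3% | 7.5 to 70.1 |

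A rule that keeps the early AITL subjects in the AITL row but leaves those from the CXCL12+ cohort in the CXCL12+ row also gives (5 + 2)/(11 + 3) = 7/14.

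- AITL shift, cohort to histology: 52.94 − 45.45 = 7.5 points.
- CXCL12+ shift when AITL is removed: 41.67 − 33.33 = 8.3 points.
- SAP 8.1 would use Wilson limits when there are more than four responders: 21.3 to 72.0 for 5/11, 31.0 to 73.8 for 9/17 and 19.3 to 68.0 for 5/12. The picture is the same.

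**What cannot be computed.** A response rate over all CXCL12+ subjects is out of reach. The documents give neither the number of CXCL12+ subjects in the AITL cohort nor response by genotype for the 8 early reference-sequence subjects.

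**Reading the rows**
- *Exclusive, by enrolment cohort.* Nobody is counted twice. The AITL row leaves out 7 of 23 AITL subjects. The CXCL12+ row includes AITL subjects and leaves out CXCL12+ subjects from the AITL cohort and from stages 1 and 2.
- *By attribute.* Each row gives its marginal rate and the rows overlap. CXCL12 status is still mixed with AITL histology.
- *Either way.* There is no CXCL12-variant row.

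**The case against.** The best defence is that the groups are the enrolment cohorts. SAP 12 summarizes by cohort, and SAP 4 sizes the AITL and CXCL12 subgroups at 12 each, which are the planned expansion cohorts. The protocol deliberately admits AITL subjects to the CXCL12+ cohort, so the rate in that cohort answers the question for which it was sized. The analyses are secondary, SAP 8.1 and 8.2 allow covariate models, and SAP 8.2 warns about small subgroups.

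Much of this stands. A cohort reading is plausible and its rates are legitimate. But no section states it, the label says genetic subtype, and 7.1 defines the residual group by histology. The small-sample warning does not mention overlap, and optional models do not supply a variant group in the planned tables.

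A reader might go further in four ways that the documents do not support:
- *Neither the AITL nor the CXCL12+ row answers its own question.* Under the attribute reading each gives its marginal rate, and under the cohort reading each describes its cohort.
- *The CXCL12+ result is really an AITL result.* Rates of 5/12 and 3/9 cannot be told apart, and there is no CXCL12-variant comparison to judge by.
- *SAP 14 flatly contradicts 2.2 and 8.2.* It can be read as covering only the pooled primary ORR. The wording is loose.
- *T-follicular-helper and follicular PTCL have no place.* The protocol's inclusion criteria admit them to the AITL cohort, and SAP 3.1 includes the related helper-cell histologies in its extension. What is unstated is whether they count in the AITL row.

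**Conclusion.** The point holds as a fault in how the secondary subgroups are specified. One variable mixes histology with genotype, the attributes overlap in enrolled subjects, no assignment rule is written, and no CXCL12-variant group is planned. On the preliminary counts the choice of grouping moves the AITL rate by 7.5 points and the CXCL12+ rate by 8.3 points. All intervals are wide and overlap, so this is about what the rows mean and does not show a difference between groups. The primary ORR, taken over the whole full analysis set, is unaffected.

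The 3/9 and 7/14 rest on inference: that the 23 AITL subjects include the four in the CXCL12+ cohort, and that three of those four were evaluable. Four evaluable (3/8) would need two subjects without CR, PR or SD in a cohort that has one. Without the enrolment constraint, two would also fit, giving 3/10 = 30.0% (6.7 to 65.2). The inferred three early AITL subjects also differ from the two that Protocol 8.1 mentions for stages 1 and 2; the documents do not explain this. The 5/11, 9/17 and 5/12 need no such inference.

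**What to change.** Before database lock, replace the single variable in SAP 2.2, 7.1, 8.1, 8.2 and 8.3 with two classifications over all full-analysis-set subjects:
- histology: AITL and T-follicular-helper type (stating that the latter count here), PTCL-NOS, other;
- CXCL12 3'UTR status: reference, variant, unknown.

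Report ORR, PFS and DOR by each. Add a descriptive histology-by-CXCL12 cross-table giving subjects and responders per cell. Show results by enrolment cohort separately, so that the stage 1 and 2 subjects who generated the hypotheses can be told apart from those enrolled to examine them. Reword the SAP 14 sentence so that it covers only the pooled primary ORR and agrees with 2.2, 8.1 and 8.2.

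The planned swab, tumor and response data supply what is needed, and subjects without a CXCL12 result go to unknown. The cost is SAP wording and a few more tables. Some cells will be very small, so the tables should be labelled descriptive.

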2.3. Exploratory Objectives and Endpoints

Exploratory Objectives	Exploratory Endpoints
Assessment of the longitudinal data on tumor assessment.	Tumor size

Exploratory Objectives	Exploratory Endpoints

Exploration of the feasibility of collecting tissue biopsies, buccal swabs, and blood samples and analyzing these biopsies and samples for the detection of biomarkers potentially related to tipifarnib activity. The biomarker analyses may include oncogene panel sequencing from tumor tissue samples, immune cytokine profiling from serum samples, and Killer cell Immunoglobulin-like Receptor (KIR) genotyping from blood samples.
 
[REDACTED]
	
Molecular results of blood, buccal swabs, and tumor tissue samples will be listed.

3. STUDY DESIGN

3.1. General Study Design and Plan

This Phase 2 study will investigate the antitumor activity in terms of ORR of tipifarnib in subjects with relapsed or refractory PTCL. Only consented subjects who meet all the eligibility criteria will be enrolled in the study. All screening evaluations will be completed within 4 weeks (28 days) of Cycle 1 Day 1. Any screening evaluation, including disease status, will need to be repeated if performed more than 4 weeks from Cycle 1 Day 1.

Up to 70 subjects may be enrolled (receive tipifarnib) in the study. The first 18 subjects may be of the following PTCL sub-types: PTCL, not otherwise specified (PTCL-NOS), angioimmunoblastic T-cell lymphoma (AITL), ALK-positive and -negative anaplastic large cell lymphoma (ALCL), hepatosplenic T-cell lymphoma, enteropathy-associate T-cell lymphoma (EATL), extranodal natural killer (NK) T-cell lymphoma, nasal type and subcutaneous panniculitis-like T-cell lymphoma. The AITL expansion cohort (N=12) will enroll only subjects with AITL.

A multi-stage study design which assumes enrollment of the patients in potentially three consecutive groups (11, 7, and up to 52 participants) will be employed. This design is intended to allow the termination of accrual in case of unacceptably low efficacy after objective responses in the first 11 evaluable subjects (Stage 1) assessed in a Full Analysis Set (FAS) basis. If 0-1 objective responses are observed after the first 11 evaluable subjects, the study will be closed to further enrollment. If 2-4 responses are observed, 7 additional subjects will be enrolled (Stage 2). Treatment will be considered of further interest if at least 4 responses are observed (out of 18 subjects).

Based on the observed antitumor activity during Stage 1 and Stage 2 of the study (2 subjects enrolled with AITL and both subjects achieved a partial response), an AITL cohort will be enrolled (N=12) according to Amendment 4 to the protocol.

Based on the observed antitumor activity during Stage 1 and Stage 2 of the study in which subjects who were found to have high levels of CXCL12 gene expression by retrospective analysis had a longer PFS compared to subjects with low expression, a CXCL12 + cohort will be enrolled (N = 12) according to Amendment 6 to the protocol.

Based on the high antitumor activity observed in AITL subjects in the AITL cohort and other portions of the study, enrolment in the AITL cohort has been expanded to include up to 20 additional subjects with tumors of AITL and related T follicular helper cell histologies in order to further characterize the safety and tolerability of tipifarnib in this relatively rare population. The selection of 20 subjects was empirical and no statistical hypotheses will be tested. Descriptive statistics will be used to report response rate.

Eligible subjects will receive tipifarnib administered at a starting dose of 300 mg, orally with food, BID on days 1 - 21 in 28-day cycles. Stepwise 100 mg dose reductions to control treatment-related, treatment-emergent toxicities are allowed and further detailed in Section 9.5. Subjects who received tipifarnib bid on Days 1 – 7 and Days 15 – 21 in 28-day cycles during the conduct of earlier versions of this protocol may remain on that dose regimen at the discretion of the investigator. Alternatively, the subject may transition to receive a dose of 300 mg, orally with food, bid on Days 1-21 of 28-day treatment cycles beginning on Day 1 of their next cycle.

Subjects may use proton pump inhibitors or H2 antagonists during the treatment portion of this study. However, subjects should be instructed to use antacids (magnesium or aluminum containing products) at least 2 hours before or after intake of oral study drug.

In the absence of emerging unmanageable toxicity, subjects may continue tipifarnib treatment for as long as the investigator considers that the treatment is providing clinical benefit up to 12 months since the subject's enrollment. Treatment may continue beyond 12 months upon agreement by the Investigator and Sponsor if there is documented evidence of sustained clinical benefit.

Tumor assessments will be performed at screening, at the Day 22 visit (\pm 5 days) performed during Cycles 2, 4, 6 and once every approximately 12 weeks (Cycles 9, 12, 15, etc.) thereafter, until disease progression. Tumor assessments will be performed more frequently if deemed necessary by the investigator. A tumor assessment will be performed upon treatment discontinuation (End of Treatment visit) if the reason for discontinuation is other than disease progression and no tumor assessment was performed in the prior 8 weeks. Subjects who discontinue treatment for reasons other than disease progression must continue tumor assessments until disease progression, withdrawal of subject's consent or initiation of another anticancer therapy. Determination of objective tumor response will be performed by the Investigator according to the Lugano Classification. Subjects who have experienced a complete response may be considered for transplantation.

Efforts will be made to collect information on the subject's response and duration of response to the last prior therapy.

Upon disease progression, all subjects will be followed approximately every 12 weeks for survival and the use of subsequent therapy until either death or 12 months after accrual of the last

study subject, whichever occurs first. Information on survival and subsequent anticancer therapy may be collected by phone.

All subjects will be followed-up for safety during treatment and up to approximately 30 days (\pm 7 days) after treatment discontinuation or until immediately before the initiation of another anti-cancer therapy, whichever occurs first. Additional follow up may be implemented until the subject recovers from any emergent treatment related toxicity or the adverse event is considered irreversible by the investigator. Target organ toxicities will be monitored via clinical and laboratory assessments using the National Cancer Institute Common Terminology Criteria for Adverse Events version 4.03 (CTCAE v 4.03).

